
Methodology
	
This is a mixed methods study with four arms.
 
 1. Patient questionnaire Patients with Rheumatoid Arthritis cared for at the Barts Arthritis Centre will be asked to complete a questionnaire about Rheumatoid Arthritis and the opportunities/barriers of technology to support care. Questions are a mixture of likert scales and tick box answers 2. Semi-structured patient interviews Patients with Rheumatoid Arthritis cared for at the Barts Arthritis Centre will be invited to participate in a ~60 minute semi-structured interview with a researcher from EECS, which will be recorded and transcribed. The interview will focus on the challenges of living with Rheumatoid Arthritis and the opportunities/barriers of technology to support care. Thematic analysis will be used to analyse qualitative data. 3. Clinician questionnaire E-questionnaires will be distributed via various Rheumatology mailing lists. Questions are a mixture of free text, tick boxes and likert scales, focussing on the opportunities and barriers of technology to support Rheumatoid Arthritis care. 4. Semi-structured clinician interviews Rheumatology Clinicians who agree to participate will be invited to participate in a ~30 minute semi-structured interview with a researcher from EMR, which will be recorded and transcribed. The interview will focus on how clinicians navigate care pathways for Rheumatoid Arthritis and the opportunities and barriers for technology to support care. Thematic analysis will be used to analyse qualitative data. 
Covid-19 sub-study The patients and clinicians who previously participated in an AtTRA interview will be invited by letter (patients) or email (clinicians) to complete a short e-questionnaire to understand whether attitudes to computer supported care have changed in light of the pandemic. Questions are a mixture of free text and likert scales.

Objectives / aims
	
The aim of this work is to determine the opportunities and barriers for intelligent mobile technology to support Rheumatoid Arthritis Care, targeted at both patients and clinicians as end users. To this end, the study seeks to

	
understand the day-to-day challenges of living with and managing Rheumatoid Arthritis, in order to design technology which meets the needs of the target users; and the expectations patients and clinicians hold for intelligent mobile technology. This understanding will be used in the short term to improve existing apps and in the longer term as a basis for how next generation mobile health technology could provide support for those directly involved in Rheumatoid Arthritis care.
 
Potential opportunities for support of patients include:
 
 • Helping patients improve quality of life • Improving clinical outcomes by achieving tighter disease control • Supporting patients' clinical decision making • Supporting patient-clinician communication • Reducing the need for direct patient-clinician contact • Patient-patient support • Educating patients • Supporting behavioural change / attitudes to the disease / disease acceptance 
The aim is to determine what, if any, contextual and cultural factors exist around the clinical pathway activities (eg around tapering, attitudes to flares, etc).
 
A Covid-19 questionnaire sub-study has been added to understand how the changes in care instituted during the pandemic may have influenced interview participants' opinions on the use of technology to support care.

Number of participants
	
This is an unpowered study so patient numbers are estimates based upon the literature.
 
Patient Questionnaire 100
 
Patient Semi-Structured Interview 15-25
 
Clinician Questionnaire 40
 
Clinician Semi-Structured interview 10-15
 
Covid-19 sub-study 15-25
 
Total 180-210

Inclusion and exclusion criteria
	
Patients Inclusion: >18 years old, no upper limit on the age range. Rheumatoid Arthritis, diagnosed by a Rheumatologist.

	
Comprehension of Patient Information Sheet and Consent.
 
Patients Exclusion: No formal diagnosis of Rheumatoid Arthritis. Insufficient English Language capability to complete the questionnaire or interview.
 
Clinicians: Doctors, Nurses or Allied Health Professionals Specialising in Rheumatology care for 1 year or more.


Statistical methodology and analysis (if applicable)
	
Due to the study type there is no statistical powering for the patient population.
 
Information from the interview studies and any open text boxes in questionnaires will be analysed using thematic analysis to code emerging themes from patient and clinician interviews and 'free text' questionnaire answers.
 
Descriptive statistics will be predominantly used to analyse the quantitative sections of the questionnaires. However, if no clear trends are identified then further statistical analysis will proceed with support of the Experimental Medicine and Rheumatology Statistician, and is likely to include the following:
 
 ● One sample t-tests will be used for Likert scales to compare the mean of scores with the central value of the score ● Chi-square or fisher's exact test to assess the associations between patient groups stratified according to demographic parameters ● Comparison of quantitative variables, two sample t-tests and nonparametric mann-whitney tests will be applied ● Multivariate analysis by binary logistic regression to examine the variables influencing the willingness to use technology.

Study duration
	
Recruitment & interviews: 18 months Analysis: 12 months

3. Introduction

PAMBAYESIAN is an EPSRC funded project that aims to develop intelligent technological support for those with chronic conditions. One strand of this project is to understand patient and clinician needs within the context of routine clinical care. This group of studies forms one strand of that work and focuses on rheumatoid arthritis: one of the PAMBAYESIAN case study areas.

Rheumatoid arthritis (RA) is the most common inflammatory arthritis affecting 1% of the population. In recent years the outcome for patients with RA has improved significantly although it remains a chronic rather than curable disease, resulting in a health economic burden to the UK of £8 Billion/annum. Good outcomes for patients are associated with tight control of disease measured through a composite disease activity score (DAS), which integrates swollen and tender joint counts, patient visual assessment score of disease activity with markers of inflammation (CRP or ESR). However tight disease control, and so good outcomes for patients, requires intensive monitoring in order to ensure timely adaptation of therapy, a situation that is frequently not possible due to limited health care resources. Remote monitoring utilising smart technology offers the opportunity to deliver frequent disease activity measures, whilst also engaging patients in disease management. There are many commercially available Apps targeted at patients with Rheumatoid Arthritis. However, systematic reviews have found these to be of limited clinical utility, rarely using validated outcome measures, and lacking capacity for information sharing with clinicians.

To date the clinical benefits of AI have disappointed. A lack of close collaboration between clinicians and engineers is an important factor. The PAMBAYESIAN project is a collaboration between computer scientists from the School of Electronic Engineering and Computer Science of Queen Mary University of London, and clinicians from the Centre for Experimental Medicine and Rheumatology / Barts Arthritis Centre, Mile End Hospital, Barts Health NHS Trust. This study aims to understand the decisions made by patients and clinical staff in routine clinical care, what the potential opportunities and barriers to technology supported care are, and the acceptability of decision aids to both clinicians and patients.

This study combines the planned work to understand opportunities and barriers to the use of technology to support sufferers of Rheumatoid arthritis from both patient and clinician perspectives. The work builds on work with the Rheumatoid arthritis PPI group. This has led to the development of initial personas of patients with rheumatoid arthritis. Personas are realistic but

fictional descriptions of potential users, which are used as design tools to ensure design focuses on the needs of the user groups the applications are intended to help.

The overall study combines patient and clinician interviews and questionnaires. A separate study (using non-NHS routes to recruit patients e.g. charities, social media; via QMUL ethics) will validate the existing personas, with people with knowledge of rheumatoid arthritis. Based on the results we will then conduct usability studies on a series of prototype interfaces. The interfaces and precise nature of the prototypes will depend on the results of these studies.

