Since the onset of the Covid-19 pandemic, remote consultations and monitoring have been rapidly instituted across rheumatology services. A short questionnaire sub-study has been added to investigate whether interview participants' opinions on the use of technology to support care delivery has changed in light of these circumstances.

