4.2. Secondary objective

1. Do the perceived opportunities and challenges vary according to patient demographics e.g. disease activity, disease duration, patient age?
2. What are the challenges of living with Rheumatoid Arthritis? (This will include issues around everyday life, flares, pain, medication and appointments from a patient perspective.)
3. Do the perceived opportunities and challenges vary according to clinician demographics e.g. age, subspeciality?
4. Are there significant differences in patient and clinician expectations for health technology assessed parameters?
5. Have the perceived opportunities and challenges changed since the rapid institution of remote care due to the Covid-19 pandemic?

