5.2. Exclusion criteria

Patients:

- Unwilling or unable to give consent
- Inability to understand written and/ or verbal English (there may be some assistance from a research assistant for Bengali speakers completing the survey; however for the interview there is no translation assistance)

Clinicians:

- Unwilling or unable to give consent
- < 1 year experience in Rheumatology as a specialism
- No longer practicing Rheumatology
- Clinicians working within Rheumatology whom do not routinely look after patients with Rheumatoid Arthritis.

Covid-19 sub-study:

- Patients and Clinicians who did not participate in an interview as part of the AtTRA study

Study design

This is a cross-sectional, mixed methods study, with four parallel arms: Patient questionnaire; Patient interview; Clinician questionnaire and Clinician Interview. Thus the study has both qualitative and quantitative aspects.

Both patient and clinician interviews are Semi-structured. They have been developed by a team of researchers from both EECS and EMR. The interview is structured with 'top' questions, which are open and broad, with sub-questions on important issues to be broached if the interviewee does not volunteer this information when asked the initial 'top' question. A single researcher from EECS will conduct patient interviews, and a single researcher from EMR will conduct clinician interviews, in order to maintain consistency. Interviews will be audio recorded and transcribed by an external transcription service (Bristol Transcription Services) previously used by EECS.

Patient and Clinician questionnaires have been developed by a team of researchers from both EECS and EMR. Patient questionnaires will be paper based with the option for postal return. Clinician questionnaires will be administered electronically.

Patients and Clinicians who participated in an interview will be contacted via letter or email and invited to participate in a brief follow up e-questionnaire (via SurveyMonkey™) regarding how the changes in care due to Covid-19 have impacted their beliefs about the use of technology to support care.

6. Study procedures

Informed Consent

Participants will be asked if they wish to participate in the study following review of a detailed patient information sheet (PIS). Consent will be implied by the decision to complete and return the questionnaire.

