For interviews, consent will be obtained by the researcher conducting the interview. A written information sheet will be provided, with a separate consent form. Interviews will be conducted on a separate date from recruitment, so patients will have a minimum of 24 hours to decide if they wish to participate.

For Clinicians, information regarding the study will be circulated via email, including a detailed participant information sheet. A link to the online questionnaire (hosted by Survey Monkey™) will be provided, and the decision to complete the questionnaire will be taken as their consent to participate. Those who express willingness to participate in the interview study will be contacted and written consent taken at the time of interview.

Patients and clinicians who participated in the interview arm of the study will be contacted via email or letter to invite them to participate in a short electronic survey (via SurveyMonkey™) regarding how the changes in care during the Covid-19 pandemic have impacted their beliefs about the use of technology to support care. Completion of the electronic questionnaire will be considered as sufficient consent to participate.

Screening and Recruitment

Patients:

Patients will be identified via outpatient clinics at Mile End Hospital and following discussion with a member of the study team will be provided with a patient information sheet. Patients will be asked to complete a questionnaire and post to return, and if participating in the interview a follow-up visit will be booked to arrange an interview at a convenient time. Patients may agree to participate in either or both arms of the patient study (i.e. questionnaire, interview, or both). Following completion of the interview the patients will have no further issues.

Clinicians:

Clinician e-questionnaires will be disseminated through the contacts of a Rheumatology Clinical Research fellow. Regional and National Rheumatology e-mailing lists will be asked to distribute the questionnaire, including North and South London and KSS (Kings Surrey Sussex) Registrar mailing lists, and the British Society of Rheumatology (BRITs) mailing list.

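### Patients can answer the Covid-19 sub-study only online, although it asks about technology in care; this risks outcome-related non-response, and a paper reply option would reduce it cheaply

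*Protocol*

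**What the plan says.** The Covid-19 sub-study follows up people already interviewed. Each place that describes how it is answered gives an electronic form:

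- Synopsis, Methodology: former interviewees are "invited by letter (patients) or email (clinicians) to complete a short e-questionnaire to understand whether attitudes to computer supported care have changed".
- Study design (after section 5.2): the follow-up questionnaire is an e-questionnaire on SurveyMonkey.
- Section 6, Informed Consent: former interviewees are contacted to "invite them to participate in a short electronic survey", and "Completion of the electronic questionnaire will be considered as sufficient consent to participate".

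No paper, telephone or assisted route is offered. The main patient survey is handled differently: "Patient questionnaires will be paper based with the option for postal return".

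The purpose, at the end of section 3.1, is to "investigate whether interview participants' opinions on the use of technology to support care delivery has changed". Secondary objective 5 (section 4.2) asks: "Have the perceived opportunities and challenges changed since the rapid institution of remote care due to the Covid-19 pandemic". Items are Likert scales and free text (synopsis). Section 7.1 sets a target of 15-25 patients and clinicians combined, resting on an expected response of about 50%.

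Patient eligibility (synopsis and section 5.1) sets no technology requirement and no upper age limit, and section 5 allows interviews on site as well as remotely. Patients who use little technology can therefore be among those invited.

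**The concern.** A patient reached by letter has to go online to reply, and completing the online form is also how consent is given. The questions concern technology in care. Whether a patient can or will reply may therefore depend on what is being measured, and about half of those invited are expected not to reply.

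Two results for objective 5 are exposed. The Likert results could describe mainly patients who are comfortable online. The free-text themes could lack the views of patients for whom remote care was itself an obstacle, which is one of the challenges the objective asks about. No later analysis can recover views that were never collected, so the time to act is before the invitations go out.

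**Working it through.** **1. The plan's own figure.** The interview arms are 15-25 patients and 10-15 clinicians (section 7.1), so 25 to 40 people can be invited. Half of that is 0.50 × 25 = 12.5 to 0.50 × 40 = 20. The stated target is 15-25, which needs 15/25 = 60% to 25/40 = 62.5% response. The stated 50% does not reproduce the target. This is a separate and minor matter, but it is a reason to show a range of response rates below.

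**2. Bias in the level of attitude among patients.** Let r be the response rate and p_R and p_N the proportions favourable among responders and non-responders. Then

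responder result − result for all invited = p_R − [r·p_R + (1 − r)·p_N] = (1 − r)(p_R − p_N).

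The Protocol gives no value for the gap; 10 to 40 points is an assumption. The 50% is stated for patients and clinicians combined; using it for patients alone is also an assumption.

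| Response r | Gap 10 points | Gap 40 points |
|---|---|---|
| 50% (stated) | 5 | 20 |
| 60% | 4 | 16 |
| 62.5% | 3.75 | 15 |
| 75% | 2.5 | 10 |

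At 50%, 15-25 patients yield 7.5 to 12.5 replies, so 5 to 20 points amounts to about 0.4 (0.05 × 7.5) to 2.5 (0.20 × 12.5) people.

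**3. Pooling with clinicians.** If clinicians respond at the same rate and without bias, the patient bias is multiplied by the patients' share of the pool. At the upper end this is 25/40 = 62.5%, so 5 to 20 points becomes 3.1 to 12.5.

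**4. Bounds with no assumed gap.** With 50% non-response, an observed 70% more favourable is compatible with 0.5 × 70% = 35% up to 35% + 50% = 85% among all invited.

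**5. Bias in the change.** Objective 5 asks about change, so the calculation in step 2 does not answer it. Let q be the share of patients with low digital access, r_L their response rate, and s_L and s_H the mean shifts in the low- and high-access groups. With overall response 50%, the low-access share among responders is w = q·r_L/0.50, and

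bias = (q − w)(s_H − s_L).

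Assume q = 20-40% and r_L = 0-25% (neither is in the Protocol). Then q − w runs from 0.20 − 0.10 = 0.10 to 0.40 − 0 = 0.40.

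| Assumed shifts (Likert points) | Bias in mean shift |
|---|---|
| s_L = 0, s_H = +0.5 | +0.05 to +0.20 |
| s_L = −0.5, s_H = +0.5 | +0.10 to +0.40 |
| s_L = +0.5, s_H = 0 (others already near the top of the scale) | −0.05 to −0.20 |

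The sign depends on which group moved more. If a non-digital route brought both groups to the same response rate (r_L = 0.50), then w = q and the bias is zero in every row.

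**The case against.** The strongest reply is that the documents show a risk and not a bias. They give no rate of digital access and no expected difference in response, and they do not attribute the expected non-response to the online form. The sub-study serves one of five secondary objectives in an unpowered, mainly descriptive study. Clinicians, up to 15 of the 40 invitees, are already surveyed electronically. Technology use is recorded for interviewees (sections 6 and 10.1), so selective response can be examined, and an analysis plan not shown here may provide for that. All of this stands, and it limits the weight of the point. It does not remove it: a comparison of responders with non-responders can reveal selection but cannot supply the missing answers.

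Some stronger readings are tempting but unsupported:

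- A reader might infer that the reported shift must be biased towards technology. Step 5 shows that the sign reverses if the under-represented patients moved more than the others.
- A reader might infer that the change from paper to online confounds time with mode. No comparison with the main paper questionnaire is planned. The sub-study is confined to interviewees, so its natural baseline is the interview, and section 6 lets a patient join the interview arm alone.
- A reader might infer that a better online response would not help. The pool is closed, so for a given gap a higher response shrinks the bias: at 75% it is half its size at 50%.
- A reader might take the paper main questionnaire as a deliberate safeguard against digital exclusion. The Protocol does not give that as its reason.

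**Conclusion.** The point holds as a risk of outcome-related non-response, confined to patients and to secondary objective 5. It rests on three facts in the Protocol: an online-only reply, an outcome that concerns technology, and an expected response of about one half.

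For the level of attitude, the bias probably favours technology, by 5 to 20 points among patients under the assumed gap and 50% response. For change, which is what the objective asks about, neither direction nor size is established. The risk to the free-text themes does not depend on direction, because patients who do not reply contribute none.

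The primary endpoint also draws on the interviews and the paper patient questionnaire, which do not depend on this form. This is a recommended improvement, not a condition for proceeding.

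**What to change.** 1. Enclose a paper copy of the same short questionnaire and a prepaid return envelope with the patient invitation letter, and keep the online link as an option.
2. Extend the consent statement in sections 6 and 8 so that returning the paper form counts in the same way as completing the online one.
3. Record the mode of completion for each reply, identified by study number.
4. Compare patient responders with non-responders on the technology-use and demographic data already collected (sections 6 and 10.1), and report patients separately from clinicians.

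The cost is printing, postage and data entry for at most about 25 patients, plus a small procedural amendment. The drawback is that replies will come in two modes, which may differ slightly in how items are answered; recording the mode makes this visible. A paper option reduces the selection linked to digital access. It does not remove non-response for other reasons.

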3.1. Background

Mobile Health (mHealth) is a rapidly growing area due to the ubiquity of smartphone technology, and the potential for these devices as monitoring and communication devices for patients with chronic diseases. The need for technology and Artificial intelligence supported care has been specified in the NHS long term plan (1). However, there is little regulation in the development of commercial apps. Two systematic reviews of commercial apps for RA patients have found that these are of limited utility, due to lack of involvement of clinicians in development (2), lack of use of validated outcome measures for monitoring, poor security features, and inability to share recorded data with clinical teams (2,3).

The need for digital health to support Rheumatoid Arthritis care is already being addressed at EMR with the development of a bespoke mobile app for patients to monitor their DAS remotely (BioT App). The app is currently being tested to ensure validity and acceptability in a pilot study.

To date, the clinical benefits of AI have disappointed. This is due, in part, to the lack of collaboration between computer scientists and clinicians. The collaborative nature of the PAMBAYSIAN project will address this need; however it is equally vital to ensure that the developed technology will meet the needs of target users: both patients and clinicians.

This questionnaire and interview based study aims to address that need, and ensure that the technology developed will be acceptable to the target groups. Whilst some work has been done to investigate the wants and needs of patients and physicians (4,5) this has involved very small numbers and focussed primarily on specific areas e.g. motion sensing data (5). A simple

questionnaire based study explored the desired features of a self-management RA app in one hundred portuguese patients (6). Our study will build on this, to explore deeper the potential opportunities and barriers of remote monitoring technology, and moreover, it will be the first study of it's kind to attempt to understand patient and clinician attitudes to Artificial Intelligence, in the form of decision support tools, in Rheumatoid arthritis care.

Since the onset of the Covid-19 pandemic, remote consultations and monitoring have been rapidly instituted across rheumatology services. A short questionnaire sub-study has been added to investigate whether interview participants' opinions on the use of technology to support care delivery has changed in light of these circumstances.

